1.5. Risk/Benefit Assessment for the Study

Crohn's disease is a progressive and potentially life-threatening disease with few treatment options, many of which result in primary or secondary nonresponse. Inflammatory bowel disease may lead to increased risk of gastrointestinal malignancies, impairment in quality of life, and ultimate need for life-altering surgery. Current treatment options are limited in ability to establish mucosal healing and clinical remission and have significant safety and efficacy limitations; for example, biologics have significant immunogenic risks and steroids are associated with increased morbidity and mortality. Remission rates are generally low when compared to placebo rates across most therapies for IBD. There remains substantial unmet need in IBD, particularly in fistulizing CD among all phenotypes of CD. Despite the high cumulative occurrence and recurrence rates and significant morbidity associated with it, there is only 1 approved therapy for fistulizing CD.

Nonclinical studies in rats and dogs identified lymphoid tissues and testes as target organs for filgotinib in long-term repeat-dose toxicity studies. Although decreased lymphocyte numbers observed in nonclinical studies have not been seen in clinical studies, hematological assessment will be performed throughout the present study to ensure this potential risk is appropriately monitored. In both rats and dogs, microscopic findings in the testes included germ cell depletion and degeneration, with reduced sperm content and increased cell debris in the epididymis and reduction in fertility in male rats. The dog was determined to be the most sensitive species. When using the mean exposure (AUC) at the NOAELs for dogs in the 26- and 39-week chronic toxicity studies, and the 39-week targeted exposure toxicity study, the exposure margins compared with the highest proposed clinical dose of 200 mg once daily are 2.5-, 1.9-, and 3.6-fold respectively, in subjects with CD. A male safety study is planned to examine the potential effect of filgotinib on sperm/ejaculate parameters. Pending those results, the use of 200 mg in males in the United States with CD or UC will be limited to subjects who have failed at least two biologic therapies (TNF α antagonists or vedolizumab). Reference is made to the IB for further information about nonclinical testicular findings.

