  - Subjects who opt out of the LTE study will return to clinic 30 days after the last dose of study drug for post-treatment safety assessments

Based on protocol eligibility criteria, subjects will be randomized into 1 of 3 treatment groups in a blinded fashion in a 2:2:1 ratio as follows:

**Treatment group 1 (n = 30):** filgotinib 200 mg and PTM filgotinib 100 mg, once daily

**Treatment group 2 (n = 30):** filgotinib 100 mg and PTM filgotinib 200 mg, once daily

**Treatment group 3 (n = 15):** PTM filgotinib 200 mg and PTM filgotinib 100 mg, once daily

Note: US males who are not dual refractory will be randomized in a 2:1 ratio to either filgotinib 100 mg or matching placebo. For the purposes of this protocol, US males who have failed at least one prior TNF antagonist AND either previously failed vedolizumab induction therapy or are concomitantly taking vedolizumab at Day 1 and present with actively draining perianal fistulae despite continued vedolizumab therapy will be considered dual refractory subjects. This assessment is based on recently published data from a subgroup analysis of the GEMINI-2 study, showing a beneficial effect of vedolizumab treatment for subjects that were randomized with actively draining perianal fistulae at baseline {Feagan 2018}.

For subjects enrolled before protocol amendment 4, treatment assignments will be stratified according to the following factors:

- Anatomy of draining perianal fistulae at screening determined by MRI (simple *versus* complex)
- Prior exposure to TNF $\alpha$  antagonist (Yes or No)
- Presence of moderately to severely active proctitis (Yes or No)

For subjects enrolled after protocol amendment 4, treatment assignments will be stratified according to the following factors:

- Anatomy of draining perianal fistulae at screening determined by MRI (simple *versus* complex)
- Receiving vedolizumab therapy concomitantly at Day 1 (Yes or No)
- Presence of moderately to severely active proctitis (Yes or No)

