##### **3.1.3. Safety Analysis Set**

The Safety Analysis Set includes all subjects who took at least 1 dose of study drug. This is the primary analysis set for safety analyses.

CCI

[REDACTED]

CCI

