### **3.4. Examination of Subject Subgroups**

There are no prespecified subject subgroups for efficacy and safety analyses.

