#### 7.1.6. Summaries of Adverse Events and Deaths

Treatment-emergent AEs will be summarized based on the Safety Analysis Set. No formal statistical testing is planned.

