##### 7.1.6.1. Summaries of AE Incidence

The number and percentage of subjects who reported at least 1 TEAE will be provided and summarized by SOC, HLT, PT, and treatment group. For other AEs described below, summaries will be provided by SOC, PT, and treatment group:

- TEAEs of Grade 3 or higher (by maximum severity)
- TEAEs of Grade 2 or higher (by maximum severity)
- All TE treatment-related AEs
- TE treatment-related AEs of Grade 3 or higher (by maximum severity)
- TE treatment-related AEs of Grade 2 or higher (by maximum severity)
- All TE SAEs
- All TE treatment-related SAEs
- All TEAEs leading to premature discontinuation of study drug

- All TEAEs leading to premature discontinuation of study
- All TE SAEs leading to death (ie, outcome of death)
- All TEAEs leading to temporary interruption of study drug

A brief, high-level summary of AEs described above will be provided by treatment group presenting the number and percentage of subjects who reported the above AEs. All deaths observed in the study will be also included in this summary.

Multiple events will be counted only once per subject in each summary. Adverse events will be summarized and listed first in alphabetic order of SOC and HLT within each SOC (if applicable), and then by PT in descending order of total frequency within each SOC. For summaries by severity grade, the most severe grade will be used for those AEs that occurred more than once in an individual subject during the study.

In addition, the following tables will be generated and summarized by PT only, in descending order of total frequency:

- TEAEs
- TEAEs of Grade 3 or higher
- TEAEs of Grade 2 or higher
- TE SAEs
- TE treatment-related AEs
- TE treatment-related SAEs
- TEAEs leading to premature discontinuation of study drug

Data listings will be provided for the following:

- All AEs, indicating whether the event is treatment emergent
- All AEs of Grade 3 or higher
- All AEs of Grade 2 or higher
- SAEs
- Deaths
- All AEs leading to death (ie, outcome of death)

- AEs leading to premature discontinuation of study drug
- AEs leading to premature discontinuation of study
- AEs leading to temporary interruption of study drug

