### 7.1.7. Adverse Events of Interest

Adverse events of interest (AEI) include infections, malignancies (excluding nonmelanoma skin cancers), nonmelanoma skin cancers, gastrointestinal perforations, major adverse cardiovascular events (MACE), and thromboembolic events. Summaries of the following treatment-emergent AEIs will be produced to enhance the analysis of safety data.

- Events of infections, presented in the following subcategories:
  - AEs of infections, utilizing all AEs in the MedDRA Infections and Infestations SOC
  - AEs of serious infections, using all AEs in the MedDRA Infections and Infestations SOC that are classified as SAEs
  - AEs of herpes zoster, utilizing a MedDRA search term (MST) list developed by Gilead
  - AEs of opportunistic infections (OIs), utilizing a narrow scope Standardised MedDRA Query (SMQ)
- AEs of malignancies, excluding nonmelanoma skin cancers, utilizing an MST list developed by Gilead
- AEs of nonmelanoma skin cancers, utilizing an MST list developed by Gilead
- AEs of gastrointestinal perforations, utilizing an MST list developed by Gilead
- AEs of MACE, utilizing a positively adjudicated event list, presented in the following subcategories (Section 7.1.7.1):
  - Cardiovascular (CV) death
  - Non-fatal myocardial infarction (MI)
  - Non-fatal stroke
- AEs of arterial systemic thromboembolism (ASTE), utilizing a positively adjudicated event list (Section 7.1.7.1)
- AEs of venous thromboembolism (VTE), utilizing a positively adjudicated event list (Section 7.1.7.1)

The number and percentage of subjects with a reported event will be summarized for each treatment group by PT for each AEI category. Data listings for AEIs will also be provided.

The number and percentage of subjects with positively adjudicated TE MACE, TE ASTE and TE VTE will be summarized by treatment group using the adjudicated category, if applicable.

A by-subject listing of subjects with potential events for adjudication (MACE, ASTE, and VTE) and their respective adjudication results will be provided.

A by-subject listing of thromboembolic history and risk factors will be provided for subjects with potential events for adjudication (MACE, ASTE, and VTE).

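### AE percentages for male-only events are taken on the whole arm, which understates them most at 200 mg; state a sex-specific denominator

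*SAP*

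**What the plan says.** SAP 7.1.6.1 sets the AE summary: "The number and percentage of subjects who reported at least 1 TEAE will be provided and summarized by SOC, HLT, PT, and treatment group". SAP 7.1.6 gives the population: "Treatment-emergent AEs will be summarized based on the Safety Analysis Set". SAP 3.1.3 defines it without regard to sex: "The Safety Analysis Set includes all subjects who took at least 1 dose of study drug". Section 7.1.6.1 does not name a denominator. Read together, the three sections imply all dosed subjects in the arm.

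SAP 3.4 adds that "There are no prespecified subject subgroups for efficacy and safety analyses". The list of adverse events of interest in SAP 7.1.7 has six categories, none of them male-reproductive.

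On allocation, SAP 1.2 (and protocol 3.3) says that "US males who are not dual refractory will be randomized in a 2:1 ratio to either filgotinib 100 mg or matching placebo". The reason is in protocol 1.5: "Nonclinical studies in rats and dogs identified lymphoid tissues and testes as target organs for filgotinib in long-term repeat-dose toxicity studies". The same section limits 200 mg in US men until a separate male safety study of sperm and ejaculate parameters reports. Protocol 9.1.3 requires that infertility risk be discussed with every male subject at consent.

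Two planned outputs bear on the point. The AE tables give counts beside percentages, and SAP 5.1 tabulates sex at birth by arm for the same Safety Analysis Set.

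**The concern.** A woman cannot have a testicular or other male-only event, so each woman in the denominator lowers the reported percentage without being at risk. If the share of men were the same in every arm, the loss would be the same too, and the comparison between arms would survive.

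Here the shares are expected to differ because of the randomization rule itself. One group made up wholly of men feeds 100 mg and placebo and never 200 mg. If the risk per man were identical in all arms, the planned table would be expected to show its lowest percentage at 200 mg, the dose that the protocol restricts in US men because of the testicular findings. The distortion runs in the reassuring direction for that dose.

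**Working it through.** **The plan's own figures.** 75 subjects at 2:2:1 give 75 × 2/5 = 30, 30 and 75 × 1/5 = 15, as stated in SAP 1.3. The documents give no figure for the share of men per arm or for the rate of male-only events, so there is no stated figure to reproduce on the point itself.

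**Inputs from the documents.** N = 75. Restricted US men split 2:1 between 100 mg and placebo; everyone else splits 2:2:1.

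**Assumed inputs (not in the documents).** Central case: 50% men, 40% US subjects, 80% of US men not dual refractory. Ranges: 40-60%, 20-60% and 60-90%. Sex is taken as independent of country, and arms are not rebalanced.

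**Formulas.** Let M be the overall share of men and f the share of all subjects who are restricted US men.

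- f = M × (US share) × (share not dual refractory)
- Share of men among everyone else: m = (M − f)/(1 − f). This is also the expected share of men at 200 mg.
- Share of men at 100 mg: [0.4(1 − f)m + 2f/3] / [0.4(1 − f) + 2f/3]. Placebo gets half of each term, so its share is the same.
- Whole-arm percentage for a male-only event = risk per man × share of men in the arm.

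**Central case.**

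- f = 0.5 × 0.4 × 0.8 = 0.16
- 200 mg: m = 0.34/0.84 = 40.5%
- 100 mg and placebo: (0.136 + 0.1067)/(0.336 + 0.1067) = 0.2427/0.4427 = 54.8%
- Ratio 40.5/54.8 = 0.74, so equal risk per man appears 26% lower at 200 mg
- Expected arm sizes: 75 × 0.336 = 25.2 at 200 mg (about 10 men) and 75 × 0.4427 = 33.2 at 100 mg (about 18 men)

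**Ends of the range.**

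| Men / US / not dual refractory | f | Men at 200 mg | Men at 100 mg and placebo | Apparent reduction at 200 mg |
|---|---|---|---|---|
| 60% / 20% / 60% | 0.072 | 56.9% | 61.8% | 8% |
| 50% / 40% / 80% | 0.160 | 40.5% | 54.8% | 26% |
| 40% / 60% / 90% | 0.216 | 23.5% | 47.6% | 51% |

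With no restricted US men (f = 0) the shares are equal and the between-arm distortion vanishes. It exists in expectation whenever f > 0 and the other subjects include women.

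**In subjects.** Take an illustrative risk of 10% per man.

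- Central case: 4.05% at 200 mg against 5.48% at 100 mg, a gap of 1.4 points. One subject is 1/25.2 = 4.0 points at 200 mg and 1/33.2 = 3.0 points at 100 mg.
- 51% case: 2.35% against 4.76%, a gap of 2.4 points. The arms are 75 × 0.3136 = 23.5 and 75 × 0.4576 = 34.3, so one subject is 4.3 and 2.9 points.

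In both cases the gap is less than one subject in either arm.

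**With a male denominator.** Equal risk per man gives the same expected percentage in every arm, whatever f and m are.

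**The case against.** The case against is strong on consequence.

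- **The numbers can be rebuilt.** Counts appear beside percentages, male-reproductive events appear under their own SOC and preferred terms, and sex is tabulated by arm. A rate per man is one division. This stands: only the percentages are distorted, and nothing is concealed.
- **The gap is small.** Chance will swamp a difference of less than one subject in a trial sized for description. This stands as to size. It does not justify a denominator known to be wrong for these terms when the right one is already in the database.
- **The male study carries the real question.** Protocol 1.5 assigns sperm and ejaculate effects to another study. This stands. A reader might infer that zero male events here would wrongly reassure about testicular safety, but spontaneously reported AEs would say little about sperm on either denominator.
- **The fix does not equalise the men.** Any US man on 200 mg is dual refractory, while US men on 100 mg or placebo are a mixture. This stands, and the table should say so.

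Two stronger readings are tempting. A reader might take SAP 3.4 to forbid analysis by sex; it says only that no subgroup is prespecified, and a sex-specific denominator is not a subgroup analysis. A reader might also treat the absence of a male-reproductive category in SAP 7.1.7 as a defect. Such events remain in the general AE tables, so that choice is largely a preference.

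**Conclusion.** The point holds as a reporting correction. The whole-arm denominator is inferred from SAP 7.1.6.1, 7.1.6 and 3.1.3, not stated outright. The direction follows from the allocation rule: percentages for male-only events are understated in every arm and, in expectation, most at 200 mg. If the arms were instead held at 30/30/15, the 200 mg arm would still be filled only from the other subjects, so the direction would not change.

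The size rests wholly on the assumed shares of men, US subjects and dual-refractory status: about 26% lower in the central case and 8-51% over the ranges. At a 10% risk per man this is less than one subject per arm. A reader might infer that the plan hides a testicular signal at 200 mg. The documents do not support that, because the counts and the number of men per arm are both reported. No AE count or efficacy result changes.

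**What to change.** In SAP 7.1.6.1, state that percentages for sex-specific preferred terms use the number of men (or women) in the Safety Analysis Set of that arm, and show that number in the table. Add a note that US men in the 200 mg arm are all dual refractory, so rates per man are descriptive and not a like-for-like comparison between arms. A grouped summary of male-reproductive events among men is optional.

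The cost is a few lines of SAP text and some programming on data already collected, with no new procedures. The small downside is that percentages in the AE tables no longer share one denominator, which the displayed number of men or women makes plain.

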### 7.1.7. Adverse Events of Interest

Adverse events of interest (AEI) include infections, malignancies (excluding nonmelanoma skin cancers), nonmelanoma skin cancers, gastrointestinal perforations, major adverse cardiovascular events (MACE), and thromboembolic events. Summaries of the following treatment-emergent AEIs will be produced to enhance the analysis of safety data.

- Events of infections, presented in the following subcategories:
  - AEs of infections, utilizing all AEs in the MedDRA Infections and Infestations SOC
  - AEs of serious infections, using all AEs in the MedDRA Infections and Infestations SOC that are classified as SAEs
  - AEs of herpes zoster, utilizing a MedDRA search term (MST) list developed by Gilead
  - AEs of opportunistic infections (OIs), utilizing a narrow scope Standardised MedDRA Query (SMQ)
- AEs of malignancies, excluding nonmelanoma skin cancers, utilizing an MST list developed by Gilead
- AEs of nonmelanoma skin cancers, utilizing an MST list developed by Gilead
- AEs of gastrointestinal perforations, utilizing an MST list developed by Gilead
- AEs of MACE, utilizing a positively adjudicated event list, presented in the following subcategories (Section 7.1.7.1):
  - Cardiovascular (CV) death
  - Non-fatal myocardial infarction (MI)
  - Non-fatal stroke
- AEs of arterial systemic thromboembolism (ASTE), utilizing a positively adjudicated event list (Section 7.1.7.1)
- AEs of venous thromboembolism (VTE), utilizing a positively adjudicated event list (Section 7.1.7.1)

The number and percentage of subjects with a reported event will be summarized for each treatment group by PT for each AEI category. Data listings for AEIs will also be provided.

The number and percentage of subjects with positively adjudicated TE MACE, TE ASTE and TE VTE will be summarized by treatment group using the adjudicated category, if applicable.

A by-subject listing of subjects with potential events for adjudication (MACE, ASTE, and VTE) and their respective adjudication results will be provided.

A by-subject listing of thromboembolic history and risk factors will be provided for subjects with potential events for adjudication (MACE, ASTE, and VTE).

#### 7.1.7.1. Cardiovascular Safety Endpoint Adjudication Committee

An independent cardiovascular safety endpoint adjudication committee (CVEAC) will be formed to periodically review and adjudicate all potential MACE and thromboembolic events in a blinded manner. To identify potential MACE and thromboembolic events, the following AEs will be sent for adjudication. Refer to the Cardiovascular Event Adjudication Committee Charter for more details.

- All AEs leading to death
- CV events (meeting seriousness criteria), utilizing an MST list developed by Gilead
- MI, utilizing a narrow scope SMQ
- Unstable angina (meeting hospitalization criteria), utilizing an MST list developed by Gilead
- Transient ischemic attack, utilizing an MST list developed by Gilead
- Stroke, utilizing an MST list developed by Gilead
- Cardiac failure (meeting hospitalization criteria), utilizing an MST list developed by Gilead
- Percutaneous coronary intervention, utilizing an MST list developed by Gilead
- Embolic and thrombotic events, utilizing a narrow scope SMQ

The CVEAC will review the above AEs, and related clinical data to adjudicate whether the criteria for MACE (CV death, MI, and/or stroke), ASTE, and VTE have been met for each AE.

#### 7.2. Laboratory Evaluations

Laboratory data collected during the study will be analyzed and summarized using both quantitative and qualitative methods. Summaries of laboratory data will be provided for the Safety Analysis Set for data collected up to the last dose of study drug plus 30 days for subjects who have permanently discontinued study drug.

The analysis will be based on values reported in conventional units. When values are below the LOQ, they will be listed as such, and the closest imputed value will be used for the purpose of calculating summary statistics as specified in Section 3.6. Test results from hemolyzed samples will not be included in the analysis, but they will be listed in by-subject laboratory listings.

A by-subject listing for laboratory test results will be provided by subject ID number and time point in chronological order for hematology, serum chemistry, urinalysis, lipid profile, and serum immunoglobulin separately. Values falling outside of the relevant reference range and/or having a severity grade of 1 or higher on the Common Terminology Criteria for Adverse Events (CTCAE) severity grade will be flagged in the data listings, as appropriate.

Hematocrit collected from local laboratories due to COVID-19 impact will not be included in the safety laboratory summary, but they will be included in the listing with a flag to indicate which records were collected at a local laboratory.

No formal statistical testing is planned.

### 7.2.1. Summaries of Numeric Laboratory Results

Descriptive statistics will be provided by treatment group for each laboratory test specified in the study protocol within hematology and chemistry panels, and also laboratory tests from lipids panel (under fasting status) including total cholesterol, low-density lipoprotein (LDL), high-density lipoprotein (HDL), triglycerides, non-HDL cholesterol (total cholesterol minus HDL cholesterol), LDL/HDL ratio, and IgA, IgM, IgG, and total Ig, as follows:

- Baseline values
- Values at each postbaseline time point
- Change from baseline at each postbaseline time point

A baseline laboratory value will be defined as the last measurement obtained on or prior to the date of first dose of study drug. Change from baseline to a postbaseline visit will be defined as the visit value minus the baseline value. The mean, median, Q1, Q3, minimum, and maximum values will be displayed to the reported number of digits; SD values will be displayed to the reported number of digits plus 1.

Median (Q1, Q3) of the observed change from baseline values for aspartate aminotransferase (AST), alanine aminotransferase (ALT), total bilirubin, alkaline phosphatase, serum creatinine, creatinine clearance, creatine phosphokinase, white blood cell count, absolute neutrophils, absolute lymphocytes, hemoglobin, platelets, fasting total cholesterol, fasting LDL, fasting HDL, total Ig, IgG, IgA, and IgM, will be plotted using a line plot by treatment group and analysis visit.

In the case of multiple values in an analysis window, data will be selected for analysis as described in Section 3.7.3.

## 7.2.2. **Graded Laboratory Values**

Modified CTCAE Version 4.03 (see Appendix 8 of the protocol) will be used for assigning toxicity grades (0 to 4) to laboratory results for analysis. Grade 0 includes all values that do not meet the criteria for an abnormality of at least Grade 1. For laboratory tests with criteria for both increased and decreased levels, analyses for each direction (ie, increased, decreased) will be presented separately.

